9.4. Data Sources

A data feasibility assessment was conducted using the Structured Process to Identify Fit-for-Purpose Data (SPIFD) framework to determine fit-for-purpose RWD sources for this study. 27 The study will use Komodo's Healthcare Map (KHM) database linked to Claritas prescription data (proprietary voxelotor claims) and Quest Diagnostics lab data. While Komodo data is de-identified, Komodo requires that all patients have tokens from the original personally identifiable information; Datavant is used for the tokenization process. These tokens are used to link the information from unique patients together from the KHM database, Claritas prescription data, and Quest Diagnostics lab data. Data sources are anchored on a closed system of administrative claims, including patient enrollment, physician, facility, and pharmacy claims. Administrative claims submitted for payment by providers and pharmacies are verified, adjudicated, and de-identified before inclusion. An initial data completeness check demonstrated full coverage for encounters based on ICD-10-CM codes and NDC on all continuously enrolled patients. Overall, claims data are expected to be a nearly complete capture of the patient's healthcare interactions, as claims restrict data inclusion to the time when patients are enrolled in both medical and pharmacy coverage. We expect minimal missing data on the treatment of interest (voxelotor) by linking the data from Komodo with Claritas Rx and high completeness of key data elements. However, guidance from Komodo recommends study periods end 9 months prior to the end of data to ensure complete capture of closed claims. Each data source is described in further detail below.

Pfizer has conducted a validation study²⁸ of RBC transfusions using the Optum Electronic Health Records and Claims Data among patients with SCD to support the use of procedure codes to identify these events in claims data, with the following objectives:

- To assess the concordance of RBC transfusion documentation based on medical claims data (ICD-10 procedure codes) compared to structured EHR data (and vice versa).
- To confirm RBC transfusions identified in structured EHR/claims data via procedures codes through clinical notes review.
- To identify and record the details of RBC transfusion administrations (specifically the reason for, type of transfusion and volume) and secondary complications of transfusions.

The results from this validation study inform the accuracy of claims data based on procedure codes in measuring RBC transfusions as an endpoint. The validation study included 13,327 patients with a documented diagnosis of SCD and at least one RBC transfusion documented in claims or EHR within the Optum Market Clarity database between January 2016 and March 2023. Among these patients, there were 46,381 RBC transfusions performed over the study period. The vast majority (91%) of these transfusions were documented in claims (42,106) with some (22%) overlap in EHR (10,394). A minority (9%) of RBC transfusions were only documented in EHR (4,275). Given these results, we believe that claims are the more reliable data source and will be used primarily for this study.

Komodo

KHM is a real-world dataset that integrates disparate sources of patient-level data to map longitudinal patient journeys. Komodo pulls de-identified, patient-level claims data from clearinghouses, payers (150+ payers including Medicare and Medicaid), and provider data

sources to follow patients as they move through the healthcare system. The patient-centric database includes both open and closed claims data and is enriched with data from EHR and other sources. Komodo's closed dataset (payer complete dataset) will be used for this analysis. Data will be included from November 25, 2018, to January 2024. The database covers all the US census regions. The all-payer claims data is fully adjudicated. Komodo is a patient-centered claims dataset that complies with the Health Insurance Portability and Accountability Act. The KHM data dictionary is included as a standalone document to this protocol.

Claritas

Claritas Rx captures patient-level data from channel partners such as specialty pharmacies, patient services hubs (including patient assistance programs), specialty distributors, claims data providers, labs and other patient services providers to enable insights into the market and patient journey. This data source contains proprietary voxelotor claims and is linked to KHM.

Quest

Quest laboratory database contains over 56 billion laboratory test results nationwide. For this study, Quest data will be linked to the KHM from November 25, 2018, through the end of data (July 31, 2024). Important baseline variables like Hb will be captured from lab data.

9.5. Study Size

The study will include all the eligible patients with an index date from November 25, 2019, until January 31, 2023. An initial sample size assessment conducted with Komodo data through September 2023 identified ~94,000 patients with SCD, and among those patients, ~7,700 were treated with voxelotor. Published information on the annual rate of transfusions for patients with SCD was the basis for estimating an expected range for the primary outcome (number of RBC transfusions PPPY during follow-up). 14,15

A conservative sample size estimate was calculated using a linear regression model with an adjustment factor of 1.65 which takes into account the variability that is introduced by applying propensity score adjustment methods.²⁹ With 185 patients treated with voxelotor and 370 matched patients not treated with voxelotor (1:2 matching ratio), the study will ensure an 80% power to detect at least a 1-unit (1 transfusion) difference between the two groups (standard deviation = 3.0) in the change in RBC transfusions PPPY from baseline to follow-up.

9.6. Data Management

After assigning the tokens to each patient across the three unique data sources (described above in Section 9.4), Komodo Health delivers the data in one delivery. The data that is delivered is a subset of the KHM data and includes patients with at least one diagnosis for SCD at any time. Komodo Health runs data quality checks across data ingestion/mastering/normalization and standardization process by developing tests of the data pipeline with data quality assurance tools.

At Aetion, as part of the data ingestion process, raw data review is routinely conducted to understand contents of the database and scientific integrity checks are performed to ensure

the contents of the data are consistent with the expected data as laid out in the applicable data usage agreement. Some of the key characteristics explored in this process include:

- Table structure (number of rows, columns, column names, etc.)
- Summary counts per table (i.e., non-missing counts, unique counts)
- Variable distribution (e.g., min, mean, median, max for numeric variables; top frequencies for categorical variables)
- Date range (min, max, and distribution over a time period)
- Missingness percentage of attributes

Raw data files as well as transformed data files are retained on the platform; rows are dropped if they do not contain dates or have start dates that are earlier than end dates. Action performs an additional deidentification step to map the raw data unique patient identifier to an Action patient identifier.

Following receipt and review of the raw data, each data cut is connected to the Aetion Evidence Platform (AEP). A data connector specification is drafted by a data scientist, which provides a map for transformation of raw data to the Aetion longitudinal patient timeline. Validation of the database connection (DBC), via double programming, is completed to ensure that the implementation of DBC logic leads to transformed data output that connects to and behaves within AEP exactly as intended. Following validation, the specification files are used to create an Aetion data dictionary for the dataset. Prior to deployment on the AEP, a manual test is conducted to check the baseline details of the dataset, the generation of measures, cohorts, and analyses, any resulting outputs, and any relevant coding systems. The test further ensures that platform features and dataset values are visible, testable, and working as expected on the front-end.

Analyses will be done within the AEP [Version 4.99.6] (Aetion Evidence Platform® 2024) or using R version 4.2.3. For analytic datasets created off platform, original (or raw) files will never be modified.

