9.2.1. Inclusion Criteria

Table 2. Summary of Inclusion Criteria

Inclusion Criteria	Assessment Period	Operational Definition	Rationale/Validated Source
Confirmed diagnosis of SCD	[Baseline]	1 inpatient medical claim with an International Classification of Diseases (ICD), Tenth Revision, Clinical Modification (ICD-10-CM) diagnosis code for SCD or 2 outpatient claims with an ICD-10-CM diagnosis code for SCD at least 30 days apart (including all genotypes as well as unknown type)	Administrative claims study ²⁰
Age between 12 and 85 years	[Index]	Age in years since year of birth	Age range covers the initial accelerated approval indication.
≥ 2 RBC transfusions	[Baseline]	At least 2 medical claims with an ICD Tenth Revision, Procedure Coding System (ICD-10-PCS) procedure code for an RBC transfusion at least 1 day apart (maximum 1 transfusion counted per day).	The subset of SCD patients who would most benefit from a reduction in RBC transfusion and necessary to measure a change from baseline to follow-up.
≥ 365 days of continuous enrollment during baseline and at least 180 days in follow up	[Baseline] [Follow Up	Both medical and pharmacy enrollment is required for observability (with a 45-day allowable gap between claims).	Observability is required to assess whether outcomes occurred and were not assumed to be missing.
≥ 180 days of continuous voxelotor use post-index (with 45-day gaps allowed) – voxelotor arm only	[Follow up]	At least 180 days of continuous voxelotor use post-index (with 45-day gaps allowed) defined using the voxelotor ship date and days supply reported on the claim— voxelotor arm only	Adequate exposure to voxelotor is necessary to evaluate the impact on RBC transfusions and other outcomes.

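### Section 9.6 states the date-integrity rule backwards: as worded it drops rows whose start date precedes the end date, the valid order for any multi-day record

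*Protocol*

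**What the plan says.** Protocol Section 9.6 (Data Management) describes how the analytics vendor takes in the data. It lists raw-data checks, which include summary counts per table, variable distributions, date ranges and missingness. It then says "Raw data files as well as transformed data files are retained on the platform" and, in the same sentence, that "rows are dropped if they do not contain dates or have start dates that are earlier than end dates".

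The next paragraph covers a separate step. A data scientist drafts a data connector specification that maps raw data to the patient timeline. Validation of that connection, "via double programming, is completed to ensure that the implementation of DBC logic leads to transformed data output" that behaves as intended, precedes a manual test of the dataset, measures, cohorts and analyses.

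Other sections show which records the rule could reach:

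- Section 9.4: "Data sources are anchored on a closed system of administrative claims, including patient enrollment, physician, facility, and pharmacy claims".
- Section 9.2.1, Table 2: at least 365 days of continuous enrolment before index and at least 180 days after it, for which "Both medical and pharmacy enrollment is required for observability". The diagnosis of sickle cell disease can be met by a single inpatient claim, and at least two baseline transfusions are required.
- Section 9.7.3: the primary outcome is the change in the annualised count of transfusions, taken from claims.
- Section 9.8.1: the analysis is to adhere strictly to the protocol.

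No other section restates or corrects the row-dropping rule.

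**The concern.** A rule of this kind exists to remove records with impossible dates. As worded, it removes the possible ones. Same-day rows survive, because equal dates are not in *earlier* order. Every dated row that spans more than one day meets the condition for deletion, and a row that ends before it starts does not.

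This matters because it is a deletion rule in the operative methods, not background text. Section 9.7 leaves the summary and statistical methods to the SAP, but Section 9.6 itself fixes this cleaning rule. If it were carried out literally on tables with start and end dates, it would act before any eligibility criterion or outcome is computed. Enrolment spans decide who enters the cohort and how long they are observed. Inpatient records contribute to the diagnosis, the two-transfusion entry criterion, the baseline and follow-up transfusion counts, and the vaso-occlusive crisis outcome (Annex Table 1).

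**Working it through.** The protocol gives no figure to reproduce here, so the check is logical: apply the rule as worded, and then with the inequality reversed, to rows of each relevant kind.

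**Inputs from the protocol**

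- Rule as worded (Section 9.6): drop a row if its dates are missing or start < end.
- Kinds of data (Section 9.4): enrolment, physician, facility and pharmacy records.
- Required enrolment (Table 2): 365 + 180 = 545 days.

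**Assumption.** Each row carries a start date and an end date. The data dictionary is a standalone document (Annex 1) and is not shown, so this layout is inferred. The five rows are constructed examples, not study data.

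| Example row | Start | End | As worded (start < end) | Reversed (start > end) |
|---|---|---|---|---|
| Same-day claim | 2020-03-01 | 2020-03-01 | kept | kept |
| 5-day inpatient stay | 2020-03-01 | 2020-03-06 | **dropped** | kept |
| 545-day enrolment span | 2019-03-01 | 2020-08-27 | **dropped** | kept |
| Impossible row, start after end | 2020-03-06 | 2020-03-01 | **kept** | dropped |
| No dates | none | none | dropped | dropped |

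The two rules agree on same-day and undated rows and disagree on every other row. In each disagreement the rule as worded gives the wrong answer.

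**What follows under different layouts**

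1. If enrolment is held as start-end spans, whether one long span or a series of shorter ones, all spans longer than a day go. No patient could then show 545 days of enrolment, and the cohort would be empty.
2. If only claim rows carry start-end dates, multi-day rows (typically inpatient) go and same-day rows stay. Transfusion counts would fall in both baseline and follow-up, and the two-transfusion criterion would select on same-day claims. The size and direction of any effect on the treatment comparison cannot be derived, because the protocol does not give the share of transfusions billed on multi-day rows in either group.
3. If rows carry a single service date, the inequality has nothing to act on and the wording does no harm. Annex Table 1 defines a transfusion by a procedure code on any claim, counted at most once a day, and Table 2 defines voxelotor use by ship date and days supply. Neither says whether the source row has a span.

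**The case against.** The strongest reply is that this is a slip in a narrative sentence and that nothing shows it was executed. Much of that stands.

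- **Gross failure would be seen.** A reader might infer from the literal rule that enrolment was wiped out and no patient qualified. The documents do not support that. Section 9.6 lists counts per table, date ranges and a pre-deployment test of cohorts, and an empty cohort could not pass those unnoticed. The amendment entry dated 27 January 2025, after the data collection date of 6 January 2025 in Section 6, also reports an exploratory finding that about 25-30% of voxelotor patients had no more than 30 days of treatment. Usable patient-level exposure data were evidently being produced. This does not prove that the rule ran in the right direction, but it fits a wording slip better than an implemented reversal.
- **Double programming.** A reader might infer that the reversed rule was itself verified by double programming. The protocol does not say so. Double programming validates the connector logic, and nothing states that the row-dropping sentence is in the connector specification. By the same token, double programming cannot be cited as having caught the error: if the specification carried the sentence, both programmers could reproduce it.
- **Table 2.** The enrolment criterion there depends on the affected records. It says nothing about date order and is not a second error.
- **Recoverability.** Raw files are retained, so a mistake, if made, could be undone.

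The objection leaves one thing untouched: the rule is wrong as stated, and no other text corrects it. A partial loss, confined to multi-day claim rows, would also be harder to notice than an empty cohort, because same-day claims would still fill the tables.

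**Conclusion.** The point holds as an error of statement. Section 9.6 gives the date-integrity rule in the wrong direction, in current text. The consequence is conditional on two things that the protocol does not show: that the code follows the sentence literally, and that enrolment or inpatient records are stored as rows with start and end dates. If both are true, valid multi-day records that feed eligibility and the transfusion count are lost and impossible rows are kept. If either is false, the effect on results is nil.

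A wording slip is the likelier explanation. The protocol supports no estimate of rows lost or of bias, and no claim that the results are affected. The point ranks as a data-management correction that should be made, below any question of design or estimation. It should still not be left standing, since the protocol commits the analysis to following it and Section 12 plans for the reports to go to FDA and EMA.

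**What to change.** In Section 9.6, change *earlier* to *later*, so that rows are dropped when dates are missing or when the start date is after the end date.

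Confirm in writing that the data connector specification and the executed code use that direction. If either is found to carry the reversed rule, rebuild the transformed tables from the retained raw files before any result is used.

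The cost is one word in the protocol, which can go in as an administrative amendment, and one check of an existing specification and its code. No change to design, endpoint, model or sample size is needed.

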9.7. Data Analysis

Detailed methodology for summary and statistical analyses of data collected in this study will be documented in the SAP, which will be dated, filed, and maintained by Pfizer. The SAP may modify the plans outlined in the protocol; any major modifications of primary endpoint definitions or their analyses would be reflected in a protocol amendment.

9.7.1. Descriptive Analysis

After identifying the populations of interest using CEM on age and calendar time, the distribution of baseline covariates will be evaluated in the 365 days prior to index. Continuous variables will be described using mean values with standard deviations and median values with interquartile range; categorical variables will be described as the number of patients and percent. For variables derived from diagnoses, procedures, and prescription codes, patients are assumed to have experienced the event of interest if the relevant code(s)

are found among their claim records. Otherwise, it is assumed that the patient did not experience the event, thus resulting in no missing data for these variables.

9.7.2. Baseline Balance

PS methods will be used to account for baseline balance of covariates between the treated group and matched controls. PS adjustment allows for the inclusion of a pre-defined comprehensive list of confounding covariates to ensure comparable exposure and referent groups, avoiding non-convergent issues of standard outcome models. PS models estimating the ATT will be considered for this analysis. An iterative approach to estimating the PS will be used.

PS Estimation

Potential covariates that affect treatment decisions or outcomes and are eligible for inclusion in the PS model are listed in Table 5.³⁰ Potential confounding covariates will be assessed for balance at baseline using absolute standard differences (ASD). Covariates with an ASD > 0.1 will be considered imbalanced and will be included in a PS model fit using logistic regression. With this approach, the PS will be modeled as the conditional probability of receiving voxelotor given the selected covariates for each individual. The PS modeling will be performed blinded of any outcome to ensure endpoints will not be assessed before a PS method is selected. Diagnostic criteria used to assess PS model estimate are described below and in Table 6. Multiple iterations of the PS model estimation may be performed depending on diagnostic evaluation results.

Use of PS in Baseline Confounder Balance

Multiple PS methods will be considered and a step-wise approach will be used to select the most appropriate method. PS matching, in which voxelotor-exposed individuals are matched to unexposed patients using variable-ratio (1:2) greedy nearest neighbor matching with a caliper, will be the primary approach.³¹ If the sample size falls below the minimum required sample size for the primary and secondary endpoint to be 80% powered during the matching process, weighting methods, such standardized mortality/morbidity ratio (SMR) weights, will be evaluated for their suitability and to preserve sample size of the exposed group. With the SMR approach, weights for the voxelotor group are equal to 1; weights for the referent arm are defined as PS/(1-PS). The distribution of SMR weights will be reviewed; truncation and trimming will be considered to account for extreme weights. If neither PS model type is deemed appropriate, a non-ATT model (overlap weights) will be considered. With the overlap approach, overlap weights are defined as 1-PS in the voxelotor arm; weights for individuals in the referent arm are defined as the PS. The distribution of overlap weights will be reviewed to evaluate the appropriate trimming threshold. PS-matching and weighting methods will be further described in the SAP.

Diagnostic Evaluation of PS Methods

An *a priori* list of diagnostic criteria will be set to ensure analytic assumptions are met before a PS method is selected. For example, ASD will be used to assess the comparability of the groups before and after the application of PS methods.³² Observations for any covariate leading to zero cells in either group may lead to an inadequate overlap between groups in

their PS distributions. Therefore, collapsing similar categories within variables if there are categories with frequencies <10% to minimize concerns for non-positivity will be considered. Further, variables with substantial non-positivity may be removed from the model (i.e., covariables with very low or zero values in either group). Patients with missing information for covariables may be excluded or imputed from the analysis set depending on the degree of missingness and the variable. When applicable, a robust variance estimator may be utilized in the outcome model(s) to account for the weighted design. Demographics and baseline clinical characteristics of patients within each study group will be described before and after the applications of PS adjustment.

The diagnostic results will be presented to the study team who will provide a final confirmation that all the necessary criteria have been satisfied. The inferential analysis phase will only begin after sign-off of the final protocol by the study team, certified by the Principal investigator (PI). More information on the methods used to balance baseline covariates can be found in SAP and in Table 6 below.

Table 6. Diagnostic Checklist

#	Diagnostic	Description	1
1	Confirm positivity of variables	PS distribution will be visually inspected and overlap in all areas of the PS distribution will be confirmed.	
		Additionally, any patients with an observation for covariates not meeting the positivity assumption and may be considered outliers. Further detail on methodology is available in SAP.	
2	Confirm PS model fit	Any covariate with no variability (i.e., a constant value across all observations) will be removed from the PS model. The PS model will be determined as not overfit if each covariate contains ≥ 12 exposed subjects. ³³ Collinear covariates will be defined as any covariates with a Pearson correlation coefficient greater than or equal to 0.7. ³⁴ Collinear variables may be removed from the PS model if large standard errors are observed because including them may lead to biased coefficient estimates. If removed, the model will be refitted. ³⁵	
3	Confirm baseline confounder balance	Balance of all potential confounders (i.e., covariates) will be confirmed for voxelotor vs referent patients. Covariate balance will be defined as an ASD ≤ 0.10. ³⁶ Balance of these variables will still be confirmed after PS matching. Should any variables with small residual imbalance remain, balance may be deemed acceptable if the variable is not a predictor of the outcome among the referent group (defined as an ASD < 0.10 when comparing the risk of the outcome to those with the variable versus those without it). This determination will be made by clinical experts or key opinion leaders on the study team. Evaluation of imbalance in outcome prediction will only be	

1/2	0	23	Dec	am	har	20	124

		conducted once at the end of the diagnostic sub-phase if all other diagnostic criteria are met. Variables with residual imbalance across the exposure and referent groups that are associated with the outcome (e.g., baseline Hb) will be included as an independent variable in the subsequent outcome model.	
4	Assess PS model coefficients for extreme values	Evaluate PS model coefficients to identify extreme coefficients which may indicate collinearity or positivity violations. ³⁷	
		Any coefficient with extreme values that strongly predicts presence or absence of the exposure of interest (i.e., potential instrumental variables) or another covariate (i.e., multicollinearity) may be dropped, combined, or re-categorized within the PS model.	

